Study Protocol

**Association Between Body Roundness Index and
Wound Healing Post-Thoracic Surgery: A Prospective
Study**

NCT ID not yet assigned

Unique Protocol ID: TJ-JRB202503009

Data:2025.05.01

Background

The thorax is a vital region of the human body, and the issue of postoperative wound healing following thoracic surgery has long been a subject of clinical concern. Thoracic surgeries—including cardiac surgery, thoracoscopic procedures, and open thoracotomy—are commonly performed for the treatment of cardiopulmonary diseases, tumors, and trauma. Although advancements in surgical techniques and medical equipment have significantly improved surgical success rates, complications such as wound infection, dehiscence, and poor cosmetic outcomes remain relatively common due to the high tension and extensive movement associated with the thoracic region[3]. Poor wound healing in the chest can have a profound impact on patients' psychological well-being, social interactions, and overall quality of life[4]. Excessive tension in soft tissues and skin is considered a key factor contributing to delayed healing and unfavorable scarring. Studies have identified gender, age, and the use of anticoagulants as risk factors for impaired wound healing, while serum lipids may play a protective role. Lipids are critically involved in modulating inflammation, angiogenesis, cellular proliferation, and tissue regeneration, all of which are essential processes in wound healing[5][9].

Obesity has emerged as a growing concern in modern medicine and now poses a serious threat to the health of a large proportion of the population. According to the *Chinese Guidelines for the Diagnosis and Treatment of Obesity*[7], both overweight and obesity exert profound negative effects on multiple organ systems, including the cardiovascular, respiratory, and gastrointestinal systems. Numerous studies have identified excessive obesity as a major risk factor for cardiovascular and cerebrovascular diseases, type 2 diabetes, and chronic kidney disease. In clinical practice, body mass index (BMI) is commonly used to assess obesity[17-19]. However, BMI has several limitations, as it cannot

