The research team conducted discussions and analyses to develop the study protocol, including inclusion and exclusion criteria and the clinical data required for statistical analysis. Clinical and follow-up data of enrolled subjects were collected through the HIS system of Tongji Medical College. Using SPSS version 26.0, subjects were grouped based on whether their wounds achieved secondary healing, and intergroup differences were analyzed to preliminarily identify potential factors associated with impaired wound healing. Subsequently, logistic regression analysis was performed to further determine risk factors influencing wound healing. Multivariate logistic regression analysis was then conducted to identify independent risk factors affecting wound healing. These findings aim to provide clinically feasible intervention strategies to promote more efficient and effective wound healing.

Participant Selection

Inclusion Criteria:

- Patients who underwent surgical treatment in the Department of Thoracic Surgery at Tongji Hospital;
- Complete clinical data and diagnostic test results available;
- Postoperative follow-up conducted regularly in accordance with medical advice, with comprehensive follow-up records;

Exclusion Criteria:

- Without surgery or transferred to other departments;

- Missing basic information;
- Failure to review on time or refusal to follow up;
- Additional surgeries within 30 days of discharge from the hospital;

Sample Size Calculation

A total of 400 patients undergoing thoracic surgery in the Department of Thoracic Surgery at Tongji Hospital, affiliated with Tongji Medical College of Huazhong University of Science and Technology, will be enrolled.

Study Procedure

The research team conducted a thorough literature review to gain a comprehensive understanding of the relevant background before initiating the study design. Inclusion and exclusion criteria, as well as the clinical data required for statistical analysis, were established accordingly. A total of 500 participants are planned for enrollment; subjects not meeting the exclusion criteria will be excluded.

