Data collection and follow-up will be conducted using the HIS system of Tongji Hospital. The variables to be collected include gender, age, height (m), weight (kg), waist circumference, abdominal circumference, hip circumference (cm), comorbidities (such as hypertension, coronary heart disease, diabetes), preoperative cholesterol, triglycerides, low-density lipoprotein (g/L), and type of surgery.

Data analysis will be performed using SPSS version 26.0. Initially, independent t-tests will be applied to compare groups based on wound healing status (healed vs. secondary healing) at 30 days postoperatively to identify potential factors associated with impaired wound healing. Variables identified as significant in univariate logistic regression analysis will be entered into a multivariate

logistic regression model. Statistical significance is set at $p < 0.05$. This analysis aims to determine independent risk factors for poor chest wound healing and to propose preventive measures accordingly, culminating in the completion of the study report.

Potential Risks and Mitigation Strategies

This study is observational in nature, with data collected exclusively by inpatient physicians at our hospital. Patient privacy will be strictly protected throughout the data collection process. If any issues related to poor wound healing arise during follow-up, the follow-up personnel will inform patients of appropriate subsequent treatment options. Patients lost to follow-up will be excluded from the study.

Data Collection and Statistical Analysis

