Upon admission, patient data including gender, age, height (m), weight (kg), waist circumference, abdominal circumference, hip circumference (cm), comorbidities (such as hypertension, coronary heart disease, diabetes), and preoperative laboratory values including cholesterol, triglycerides, and low-density lipoprotein (g/L) will be collected. Postoperatively, data on the surgical procedure and routine pathological findings will be recorded. Wound healing status will be assessed during a follow-up visit 30 days after surgery. Group comparisons based on wound healing status (healed versus secondary healing) at 30 days will be performed using independent t-tests. Potential factors influencing wound healing will be evaluated using logistic regression analysis. Variables demonstrating statistical significance in univariate analysis will be included in a multivariate logistic regression model. A p -value < 0.05 will be considered statistically significant. This analysis aims to identify independent

risk factors associated with poor chest wound healing and to propose feasible preventive measures accordingly.

References

- [5] Schlager JG, Hartmann D, Wallmichrath J, Ruiz San Jose V, Patzer K, French LE, Kendziora B.

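### Body Roundness Index, the title exposure, gets an adjusted estimate only if its own crude test reaches p < 0.05

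*Protocol*

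**What the plan says.** The Study Procedure section of the protocol sets out the analysis in steps. First, "independent t-tests will be applied to compare groups based on wound healing status". Then "Variables identified as significant in univariate logistic regression analysis will be entered into a multivariate" logistic model, with significance at p < 0.05. Data Collection and Statistical Analysis repeats the rule: "Variables demonstrating statistical significance in univariate analysis will be included in a multivariate logistic regression model".

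Study Design gives the multivariable step its purpose: "Multivariate logistic regression analysis was then conducted to identify independent risk factors affecting wound healing". It offers no other way into the model. Study Procedure adds what the result is for: "This analysis aims to determine independent risk factors for poor chest wound healing and to propose preventive measures accordingly".

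BRI is the only exposure in the title. The Objective lists it among several factors. No section exempts it from screening, fixes a set of adjustment variables, or plans a separate adjusted analysis of BRI. The Background already states that "Studies have identified gender, age, and the use of anticoagulants as risk factors for impaired wound healing". Sex and age are collected ("The variables to be collected include gender, age, height (m), weight (kg), waist circumference, abdominal circumference, hip circumference (cm" and so on), and the same list ends with "low-density lipoprotein (g/L), and type of surgery".

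**The concern.** Whether the title question gets an adjusted answer depends on the crude p-value of the exposure itself. Three consequences follow if the rule is applied as written.

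1. Every study gives a crude BRI odds ratio, but only some give an adjusted one. A null result, or one masked by confounding in the opposite direction, stays unadjusted.
2. The adjusted BRI odds ratios that are reported have passed a significance filter. With few events, such estimates are too large on average.
3. Age and sex stay or go by crude p-value, although the protocol itself calls them risk factors.

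The protocol intends to name independent risk factors and propose prevention from this model, so the rule bears directly on the study's main conclusion.

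**Working it through.** **Reading check.** Study Procedure and Data Collection and Statistical Analysis state the same entry rule. Study Design describes the multivariable model without an entry rule. The only significance level given is 0.05 (two-sided assumed here). The preceding t-test does not alter the gate: in simulation it agreed with the univariate logistic test for BRI in 99-100% of studies.

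**Inputs.** From the protocol: alpha 0.05, and N = 400 (Sample Size Calculation) or 500 (Study Procedure). It gives no event rate, effect size or correlation, so those below are assumptions.

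**Chance that BRI passes the screen, by formula.** For a standardised covariate with event rate p,

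P(enter) ≈ Φ(√(N·p·(1−p))·ln OR − 1.96) + Φ(−√(N·p·(1−p))·ln OR − 1.96).

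With N = 400 and p = 0.10, √(400 × 0.1 × 0.9) = √36 = 6.
- OR 1.3: 6 × 0.262 − 1.96 = −0.39, so about 35%.
- OR 1.5: 6 × 0.405 − 1.96 = 0.47, so about 68%.
- OR 1.0: 5%.

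Over N 400-500 and p 5-20%, the chance is 21-65% at OR 1.3 and 42-95% at OR 1.5.

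**Simulation of the whole rule.** Settings: n = 400; BRI standard normal, true OR 1.5 per SD; age OR 1.4 per SD; sex OR 1.6; each linked to BRI at correlation r; binary surgery type (30%), OR 2.0, independent of BRI. Each term is tested alone and those that pass are refitted together. The comparison is a full model with all four forced in. There were 4,000 studies per setting, and mean ORs are geometric.

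| Quantity | r | 3% events | 5% | 10% | 20% |
|---|---|---|---|---|---|
| BRI gets an adjusted OR (% of studies) | 0 | 27 | 40 | 64 | 86 |
| | +0.3 | 45 | 65 | 89 | 98 |
| | −0.3 | 13 | 18 | 30 | 46 |
| Mean adjusted OR on entry | 0 | 2.20 | 1.89 | 1.66 | 1.55 |
| | +0.3 | 2.07 | 1.79 | 1.59 | 1.52 |
| | −0.3 | 2.09 | 1.86 | 1.62 | 1.52 |
| Full model, same entering studies | 0 | 2.24 | 1.90 | 1.67 | 1.56 |
| | +0.3 | 1.99 | 1.74 | 1.57 | 1.52 |
| | −0.3* | 2.47 | 2.11 | 1.86 | 1.69 |
| Full model, studies left unadjusted | 0 | 1.32 | 1.30 | 1.27 | 1.23 |
| | +0.3 | 1.22 | 1.17 | 1.12 | 1.07 |
| Significant in full model, no adjusted OR under the rule (%) | 0* | 2 | 3 | 3 | 3 |
| | +0.3* | 0.5 | 0.1 | 0 | 0 |
| | −0.3 | 12 | 18 | 29 | 36 |
| BRI always kept, age and sex screened: mean OR | +0.3 | 1.62 | 1.58 | 1.54 | 1.52 |
| | −0.3 | 1.34 | 1.35 | 1.36 | 1.39 |

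*Separate run, 1,500 studies per setting.

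Over all studies the full model averages 1.51-1.53, with 95-96% interval coverage. The excess on entry is therefore selection: the full model shows much the same excess or more in the entering studies. Screening age and sex alone causes no bias at r = 0.

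**Other settings.**
- n = 500, OR 1.5: BRI enters in 33/50/73/92% at r = 0, with OR on entry 2.02/1.79/1.60/1.53.
- n = 400, OR 1.3, r = 0: enters in 14/22/31/51%, OR on entry 2.07/1.81/1.57/1.43.
- n = 400, OR 2.0, r = 0: enters in 61/82/98/100%, OR on entry 2.44/2.17/2.04/2.00.

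**Second simulation with a different set-up** (n = 400, 10% baseline rate, true OR 1.3, one confounder with OR 1.6). At r = 0, BRI enters in 36% of runs with median OR 1.52 on entry, against 1.31 when always entered. At r = −0.3 it enters in 12% with median 1.70. The always-entered model has median 1.30 and is significant in 34%.

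**The case against.** The wording of the rule is not in dispute, but its scope and size can be argued.

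- **The hidden-association harm depends on the sign of confounding.** It reaches 12-36% of studies only at r = −0.3; at 0 it is about 2-3%, and at +0.3 close to nil. Nothing in the protocol says BRI is inversely related to other risk factors. This stands, so that harm is conditional.
- **At r = −0.3 the forced model is further from 1.5 in the studies where BRI enters** (2.47 to 1.69, against 2.09 to 1.52 under the rule). This also stands. Forced entry does not shrink any single result; it is right over all studies because all are reported.
- **Screening age and sex matters little at 0 or +0.3 once events reach 10%.** True. The bias persists only under inverse correlation.
- **BRI as primary exposure is inferred from the title.** The Objective gives an open list, and the analysis sections never name BRI. For a general search for risk factors, screening is poor but ordinary. Naming BRI as primary therefore sharpens the stated objective. This does not rescue the rule: BRI is still the only exposure in the title, and any listed factor faces the same gate.
- **An unseen analysis plan might force BRI in.** It would then depart from a rule that the protocol states twice.
- **Collinearity with BMI and sparse events are separate problems.** They are, but they affect how the replacement model should be written.

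**Conclusion.** The concern holds and should be fixed. The structural fault follows from the wording alone: the title exposure has no guaranteed adjusted estimate, and any it gets has been selected for significance.

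How much this matters depends on assumptions the protocol cannot settle. It is substantial with few events or a modest effect. For example, at n = 400, OR 1.5, 5% events and no correlation, 60% of studies (100 − 40) would have no adjusted BRI result, and the rest would average 1.89. At zero or positive correlation the distortion nearly vanishes with many events or a strong effect (OR 2.0 at 10% events: 2.03-2.04 on entry). The worst case, a real association left unadjusted, needs an inverse relation between BRI and other risk factors.

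**What to change.** In Study Procedure and in Data Collection and Statistical Analysis:

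1. Name BRI, continuous and per SD, as the primary exposure.
2. Fit one prespecified logistic model containing BRI and a short covariate set chosen on subject-matter grounds from data already collected, for example age, sex and type of surgery, whatever the univariate p-values.
3. Report the BRI odds ratio with its 95% interval whatever its significance.
4. Keep the t-tests and the screening of other factors as exploratory.
5. For the primary estimate, leave BMI and waist-to-hip ratio out of the BRI model. Fit them separately, and label any joint model as a secondary question. At 10% events and an assumed BRI-BMI correlation of 0.6, 0.8 or 0.9, a joint model multiplies the BRI standard error by 1.24, 1.65 or 2.27.
6. Limit the parameters to what the events allow, and use Firth penalisation if events are few.

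**Cost.** A few sentences and, for these covariates, no new data. Anticoagulant use, which the Background also names, is not in the list of collected variables; adjusting for it would need extra data.

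The forced model's standard error was 2-12% larger than the unadjusted one. Intervals are wide either way with few events: at n = 400 and OR 1.5, about 0.8-2.9 at 3% events and 1.0-2.2 at 10%. Events per parameter at 3% are 400 × 0.03 = 12, so 12/4 = 3, or 12/5 = 2.4 if type of surgery has three levels; at 5%, 20/4 = 5 or 20/5 = 4. Firth fits gave mean ORs of 1.49-1.50 with 94-95% coverage in the four-parameter model. If SPSS 26.0 does not offer the method, a second package is needed.

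### Anticoagulant use is named in the Background as a risk factor for impaired healing but is in neither collection list, so adjustment for it is not planned

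*Protocol*

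**What the plan says.** The Background of the protocol summarises earlier work: "Studies have identified gender, age, and the use of anticoagulants as risk factors for impaired wound healing, while serum lipids may play a protective role". That sentence names four factors.

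Two sections then list the data to be collected.

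- Study Procedure opens its list with "The variables to be collected include gender, age, height (m), weight (kg), waist circumference, abdominal circumference, hip circumference (cm" and ends it with "comorbidities (such as hypertension, coronary heart disease, diabetes), preoperative cholesterol, triglycerides, low-density lipoprotein (g/L), and type of surgery".
- Data Collection and Statistical Analysis opens with "Upon admission, patient data including gender, age, height (m), weight (kg), waist circumference, abdominal circumference, hip circumference (cm", continues with "comorbidities (such as hypertension, coronary heart disease, diabetes), and preoperative laboratory values including cholesterol, triglycerides, and low-density lipoprotein (g/L) will be collected", and adds: "Postoperatively, data on the surgical procedure and routine pathological findings will be recorded".

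Neither list names anticoagulants or any other drug. The criteria under Participant Selection do not mention anticoagulants either.

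For the model, the entry rule is: "Variables demonstrating statistical significance in univariate analysis will be included in a multivariate logistic regression model". Both Study Procedure and Data Collection and Statistical Analysis say that the result is to be read as independent risk factors and used to propose preventive measures.

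**The concern.** A factor that the protocol itself links to impaired healing is neither planned for measurement nor held constant by eligibility. Anticoagulant use plausibly goes with age, cardiovascular disease and central adiposity. If it does, part of an association between healing and body roundness index, coronary disease or lipids could reflect anticoagulant use, and it would still be reported as independent.

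A statistical analysis plan cannot put this right, because it can only govern variables that have been collected. The collection lists sit in this protocol.

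**Working it through.** **Step 1. Compare the Background sentence with the two lists and the criteria.**

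| Factor in Background | Study Procedure list | Data Collection list | Eligibility restriction |
|---|---|---|---|
| Gender | yes | yes | none |
| Age | yes | yes | none |
| Serum lipids | yes | yes | none |
| Anticoagulant use | no | no | none |

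Anticoagulant use is the only one of the four that is missing. Coronary heart disease is collected but is only a partial stand-in, since anticoagulants are also given for other reasons.

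**Step 2. Follow the model-entry rule.** A variable enters the multivariable model only if it is significant in univariate analysis. A variable that is not collected cannot be screened, so it cannot enter.

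**Step 3. Illustrate the size.** The protocol gives no prevalence or effect for anticoagulants and no expected rate of secondary healing. There is no planned figure to reproduce, and every input below is an assumption. In both calculations the true association of the exposure with healing is null.

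*(a) Risk-ratio scale.* Crude ratio = [p1(RR − 1) + 1] / [p0(RR − 1) + 1], where p1 and p0 are the proportions using anticoagulants among exposed and unexposed patients, and RR is the anticoagulant effect.

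| RR | 10% v 5% | 20% v 10% | 30% v 10% |
|---|---|---|---|
| 1.5 | 1.024 | 1.048 | 1.095 |
| 2 | 1.048 | 1.091 | 1.182 |
| 3 | 1.091 | 1.167 | 1.333 |

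The smallest is 1.05/1.025 = 1.024 and the largest is 1.6/1.2 = 1.333.

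*(b) Odds-ratio scale.* Assume a 6% risk in non-users.

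- Odds in non-users: 0.06/0.94 = 0.0638.
- With an anticoagulant odds ratio of 2, odds in users are 0.1277, a risk of 0.1132. With an odds ratio of 3, odds are 0.1915, a risk of 0.1607.
- Group risk = (1 − p) × 0.06 + p × (risk in users).

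For use of 10% in the low and 25% in the high body-roundness group, with an odds ratio of 2:

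- low: 0.9 × 0.06 + 0.1 × 0.1132 = 0.0653
- high: 0.75 × 0.06 + 0.25 × 0.1132 = 0.0733
- crude odds ratio: (0.0733/0.9267) / (0.0653/0.9347) = 1.13

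| Use, low v high | Anticoagulant OR 2 | Anticoagulant OR 3 |
|---|---|---|
| 10% v 25% | 1.13 | 1.24 |
| 5% v 30% | 1.23 | 1.43 |

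Taken together, the assumed scenarios give crude ratios from about 1.02 to 1.43. None is adjusted for age or comorbidity.

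**The case against.** Several points on the other side are fair.

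- **The lists are not closed.** They are introduced by words meaning that the items are included, and the data come from the hospital information system, where medication records may be retrievable. A reader might infer that the model cannot adjust for anticoagulant use. The protocol does not support that; it supports only that adjustment is not planned. Open wording does not secure systematic collection, however, and the same omission occurs in both lists.
- **The Background is a literature remark.** A reader might take anticoagulant use to be an established risk factor that the protocol has promised to study. It says only that studies have identified it, and the Objective does not list it among the factors to be analysed. What remains is a mismatch between the protocol's own account of risk factors and its data plan.
- **The illustrated ratios are crude.** Age, hypertension, coronary disease and diabetes are collected and would absorb part of the effect, though under the entry rule only those significant in univariate analysis enter the model. The ratios should not be read as estimates of residual bias.
- **Random error is also large.** With the inputs of (b) and an assumed 200/200 split of the 400 patients given under Sample Size Calculation, the standard error of the log odds ratio is about 0.38 to 0.39. The illustrated biases run from ln 1.13 = 0.12 to ln 1.43 = 0.36, below one standard error in each case. This limits the practical weight of the bias but does not remove it.
- **No safety gap follows.** A reader might infer that a wound-safety risk goes untracked. The study is observational, assigns no treatment and names no such safety item.

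**Conclusion.** The point holds as a gap in planned adjustment. Anticoagulant use is named in the Background, absent from both lists, unrestricted by eligibility, and so outside the model as written. Associations reported as independent may be partly confounded by it.

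The size cannot be derived from the protocol. The range of about 1.02 to 1.43 for a true null rests wholly on assumed prevalences, anticoagulant effects and, for the upper figures, a 6% risk. It is crude, and less should remain after adjustment for age and comorbidities. Confounding also requires that anticoagulant use be related to the exposures studied, which is plausible but not shown in the document. The bias may be small or material, and without the variable the study cannot tell which.

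**What to change.** Add pre-operative anticoagulant use to the lists in Study Procedure and in Data Collection and Statistical Analysis, as a yes/no item at admission taken from the medication record in the hospital information system. Name it as a prespecified covariate in the multivariable model, included regardless of its univariate p-value. This exception to the entry rule is needed because collecting the variable would not by itself ensure adjustment.

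If post-operative use is recorded as well, keep it as a separate descriptive item. It is not a baseline variable and may follow from complications.

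The cost is one extra field and one extra model parameter. The parameter matters somewhat if events are few: at the assumed 6% risk, 400 patients would give 0.06 × 400 = 24 events. The change concerns data capture and analysis only and implies nothing about how patients are treated.

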distinguish between lean body mass and fat mass, nor can it accurately reflect fat distribution throughout the body[7][21]. Recent research by Xiaoqian Zhang and colleagues has shown that the Body Roundness Index (BRI), a novel anthropometric measure, is closely associated with all-cause mortality in the U.S. population. Similarly, the Weight-Adjusted Waist Index (WWI) has gained increasing attention as a new parameter for evaluating body composition, due to its improved accuracy in estimating fat content and its strong correlation with various metabolic risk factors[22].

Recent studies have further confirmed that the Weight-Adjusted Waist Index (WWI), as an indicator of body fat distribution, demonstrates superior predictive value for various conditions, including cardiovascular and cerebrovascular diseases, chronic kidney disease, and urgency urinary incontinence (UUI)[17][23][24]. Despite advances in medical technology and a growing understanding of wound healing among healthcare professionals, postoperative wound complications remain a persistent issue. Although numerous new techniques, materials, and management strategies have been developed to promote wound healing, the incidence of poor wound healing continues to be a significant clinical concern[1][2][9][10].

Objective

By analyzing the associations between factors such as height, smoking history, age, BMI, BRI, waist-to-hip ratio, and lipid profiles with postoperative wound healing, this study aims to elucidate how these variables influence the wound healing process. Understanding these relationships will help identify novel therapeutic targets and support the development of innovative interventions to promote more efficient and effective skin wound healing.

Study Design

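### Preoperative lipids are studied as factors that influence wound healing, but lipid-lowering treatment is not collected, so the lipid odds ratios can be confounded by treatment and its indications

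*Protocol*

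**What the plan says.** The Background reports, as prior literature, that age, gender and anticoagulant use are risk factors for poor healing, "while serum lipids may play a protective role". The Objective lists seven factors, lipid profiles last, and says that "this study aims to elucidate how these variables influence the wound healing process". The intended use goes beyond description: "Understanding these relationships will help identify novel therapeutic targets".

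The data to be collected appear twice. Study Procedure lists "preoperative cholesterol, triglycerides, low-density lipoprotein (g/L), and type of surgery" after demographics, body measurements and comorbidities. Data Collection and Statistical Analysis says that "preoperative laboratory values including cholesterol, triglycerides, and low-density lipoprotein (g/L) will be collected". Both lists give hypertension, coronary heart disease and diabetes as examples of comorbidities. Neither names a medication, and no eligibility criterion or analysis step deals with patients on lipid-lowering treatment.

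In both sections a variable enters the multivariable logistic model only if it is significant in univariate analysis, at p < 0.05.

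**The concern.** A single preoperative lipid value means different things in treated and untreated patients. In a treated patient it is the underlying level minus the treatment effect. Treatment is also not random: it marks vascular or metabolic disease, which may itself impair healing. If treated patients end up with lower lipids than the rest, low lipids flag high-risk patients and higher lipids appear to protect, even with no lipid effect at all. This is confounding by indication.

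The stake is interpretive. A lipid odds ratio below 1 could be reported as an independent factor and carried into therapeutic targets and preventive measures. A later analysis plan cannot adjust for a field that was never collected.

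**Working it through.** The protocol gives no lipid effect, event rate, comorbidity prevalence or treatment prevalence, so it has no figure to reproduce. From it come only the variable lists, the univariate screen, the 0.05 level and the two enrolment figures (400 under Sample Size Calculation, 500 under Study Procedure). Every other input below is an assumption.

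**1. Sign of the bias.** Let a share p be treated, with healing-failure risk r1 if treated and r0 if not. Let lipids have no effect, with SD s within each group. Let d = (starting excess of treated patients) − (lowering by treatment). To first order:

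log OR per unit ≈ d·p(1−p)(r1−r0) / {[s² + p(1−p)d²]·m(1−m)}, where m is the overall risk.

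Take p = 0.20, s = 0.8, r0 = 0.08, r1 = 0.16, so m = 0.096 and m(1−m) = 0.0868; lowering is 1.0.
- Start +0 (d = −1.0): −0.0128/(0.80 × 0.0868) = −0.184, OR 0.83.
- Start +0.5 (d = −0.5): −0.0064/(0.68 × 0.0868) = −0.108, OR 0.90 (simulation 0.89).
- Start +1.0 (d = 0): OR 1.00.
- Start +1.3 (d = +0.3): 0.00384/(0.6544 × 0.0868) = +0.068, OR 1.07.

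Simulated values for risk ratios r1/r0 of 1.5, 2 and 3 are 0.91/0.83/0.73 at +0, 0.94/0.89/0.83 at +0.5, about 1.00 at +1.0, and 1.04/1.07/1.13 at +1.3. The sign is the sign of d, which the protocol does not let anyone observe.

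**2. What the recorded comorbidities do.** Step 1 leaves them out, so it overstates the problem. A fuller simulation assumed:
- a recorded comorbidity in 25% (OR 3 for poor healing);
- unrecorded severity or vascular risk in 25% (OR 1, 2 or 3);
- treatment in 5%, 37.5% or 70% of patients with neither, one or both;
- 8% poor healing with neither;
- equal starting lipids, and no true lipid or treatment effect.

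| Lowering (SD) | Unrecorded-risk OR | Lipid OR per SD: crude | + comorbidity | + comorbidity + treatment |
|---|---|---|---|---|
| 0.5 | 1 | 0.965 | 1.001 | 1.001 |
| 0.5 | 2 | 0.942 | 0.976 | 0.999 |
| 0.5 | 3 | 0.935 | 0.967 | 1.004 |
| 1.0 | 1 | 0.940 | 1.006 | 1.007 |
| 1.0 | 2 | 0.900 | 0.959 | 0.995 |
| 1.0 | 3 | 0.881 | 0.936 | 1.000 |
| 1.5 | 1 | 0.916 | 0.998 | 0.996 |
| 1.5 | 2 | 0.879 | 0.953 | 1.001 |
| 1.5 | 3 | 0.853 | 0.920 | 1.000 |

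False significant protective findings (nominal 2.5%) occurred in about 4–28% of crude analyses at N = 400 and 4–33% at N = 500. With comorbidity adjustment and unrecorded risk present, the figures were about 2–10% and 3–12%. With treatment added they were 1.5–4.2%, where simulation error is about 0.6 points (√(0.025 × 0.975/600)).

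**3. On an LDL scale with SD 0.8.** With lowering 1.0, start 0 to +0.5 and no true effect, the odds ratio per unit is about 0.86 to 0.96 crude, 0.91 to 1.00 with comorbidity, and about 1.00 with treatment. Putting the step 2 inputs on this scale gives 0.84 to 0.94 crude and again 0.91 to 1.00 adjusted. The protocol labels LDL in g/L; a per-unit figure depends on the unit, the per-SD figures do not.

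**4. Will the comorbidity stay in the model?** Take a true comorbidity OR of 2, 25% prevalence and 8% poor healing without it, hence 14.8% with it. At N = 400 the expected cells are 14.8, 85.2, 24 and 276. The SE of the log OR is √(1/14.8 + 1/85.2 + 1/24 + 1/276) = 0.353, and z = 0.693/0.353 = 1.96, so it passes the screen about 50% of the time. Simulation gives 50% at N = 400 and 56% at N = 500; at 10% prevalence, 31% and 36%.

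**The case against.** Several objections stand, and they limit the point.

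- A reader might infer that the protocol expects a protective lipid effect and that the bias must favour it. The text does not support this. The Background only says lipids may protect, citing prior work, and the Objective gives no direction. The direction also depends on starting lipids: patients treated because their lipids were high may still have equal or higher values on treatment.
- A reader might take 0.73, or lower, as the size of the problem. That comes from a model without the recorded comorbidities and with equal starting lipids. In it treatment is the only marker of risk, so the return to 1.00 on adding treatment is built in. If the recorded comorbidity carries all the extra risk, adjusting for it already gives 1.00.
- The documents do not say how common lipid-lowering treatment is in this cohort.
- The univariate screen is a general weakness affecting every exposure. It matters here only because it may drop the variables that would remove part of the bias.
- The lists are open-ended and the data come from the hospital information system, so medication could still be extracted. Nothing plans it, however. The Background itself names a drug class as a risk factor, yet no medication is listed.

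The objections do not remove the gap: without the treatment field, nobody can tell which of these cases applies.

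**Conclusion.** The point holds as a conditional one. As written, the plan can confound the lipid odds ratios with treatment and its indications. They look spuriously protective if on-treatment lipids are lower than untreated patients' lipids; the bias is null if they are equal and reversed if they are higher. Adjusting for recorded comorbidities removes all or part of it, provided they survive the univariate screen.

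Under the assumed inputs, the residual odds ratio after comorbidity adjustment is about 0.91 to 1.00 per unit LDL. That is modest, but enough to raise false protective findings from 2.5% to at most about 10–12% in the scenarios examined. None of these sizes can be derived from the documents. Lipids are one of several factors and Body Roundness Index is the title exposure, so the priority is low to moderate.

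**What to change.** - Add lipid-lowering therapy at admission (yes/no and class), taken from the hospital information system, to the variable lists in Study Procedure and in Data Collection and Statistical Analysis.
- In the multivariable model for each lipid variable, keep this field and the recorded comorbidities regardless of their univariate p-values.
- Repeat the lipid analysis in patients not on such therapy, as a sensitivity analysis rather than as a condition for reporting.
- Describe lipid results as associations, and align the Objective's wording on influence and therapeutic targets with that.

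The cost is one extra data field from a system already in use, one covariate, and a somewhat wider interval for the lipid odds ratio, most of all in the untreated subset. The change concerns data and analysis only, not patient care.
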